7.1 Overall framework

Study monitoring is conducted to ensure that the rights and well-being of trial participants are protected, that the reported trial data are accurate, complete, and verifiable, and that the conduct of the trial is in compliance with the currently approved protocol/amendment(s), with International Conference on Harmonization Good Clinical Practice (ICH GCP), and with applicable regulatory requirement(s)

7.2 Roles & responsibilities for regular operations

PI: The PI will meet with study staff on a weekly basis to monitor the progress of the study. During phases when subject recruitment is occurring, the PI will review screenings and scheduling of assessments, as well as strategies to improve recruitment yield at weekly meetings with the study team. Issues such as maintaining confidentiality and privacy of participants during screening, assessment and data collection, protocol deviations and adverse events will be reviewed. For serious adverse events, the PI will be notified as soon as the SAE comes to the attention of study staff.

Study coordinator/research assistant: This bachelors level individual will carry out the screening and informed consent, and they will provide additional study information, all under the supervision of the PI. The individual will be trained in screening, administering consent and information to the participants. Questions about eligibility will be discussed with the PI.

7.3 Frequency and type of other study monitoring

Institutional Review Board monitoring: Approval of all procedures, advertisements and materials given to subjects will be secured from the University of Michigan IRBMED. Annual reviews will be conducted by IRBMED, including the number of subjects screened, enrolled and withdrawn. The IRB will also review protocol deviations, adverse events (according to the reporting timetable of IRBMED) and complaints that arise in connection with the study.

Data monitoring: Data entry will be audited by study staff, who were not involved in primary data entry. Patient questionnaire data will be entered largely through electronic data capture, e.g., REDCap. Research data will be maintained on password protected computers, behind UM firewalls. All enrolled participants will receive participant identifiers, which will be used to code all research records for this project. Paper records with no identifying data beyond the research code are stored in locked cabinets. Copies of executed consent forms will be stored in separate locked cabinets. Demographic data will be entered into spreadsheets, and behavioral data will be merged into files. Password-protected electronic files separated from the research data will track consents, including the link between the research identifier and individual participants. This tracking file will be the sole link between participant identifiers and research data. By deleting the field linking identifiers with participant names, research records can be effectively anonymized.

7.4 Management of withdrawals and drop-outs

When participants drop out during the assessment, but before enrollment, all data will be destroyed. The consent form will be retained until study closure for regulatory purposes. Limited, de-identified data regarding ethnicity, age, gender, and diagnosis will be retained through the screening process in order to establish the sampling frame. If a participant drops out due to substance use but would otherwise meet the inclusion criteria, all data will be retained until the closing of the project, in case the participant becomes eligible and wishes to be reconsidered for the study before conclusion of recruitment. When participants drop out after enrollment, data may be destroyed, depending upon the wishes of the participant. However, consent forms and the research number will be retained.

8. Benefits/Risks

8.1 Benefits

Participants will be taught cognitive reappraisal, an evidenced-based emotion regulation skill. Previous work has found a brief single-session CR training to be of benefit to healthy individuals and those with anxiety (e.g., Dryman & Heimberg, 2018¹⁴). Thus, in our study, some may find participation to be a positive experience, and some may experience reduced negative affect, however, participants will be informed that the primary purpose of the study is not to directly benefit participants, but to inform our scientific understanding of the neural basis of cognitive reappraisal and the effects of real-time fMRI

neurofeedback. This information will be used to design new or improve existing treatments, which may benefit those with psychiatric disorders in the future.

8.2 Risks

8.2.1 Subject Confidentiality

Measures to protect patient privacy. Study staff will make every effort to limit identifiable information on potential subjects during recruitment. Conversations in which a patient's name must be mentioned, e.g. to determine potential eligibility, will occur in private settings of the clinic. The minimum amount of information will be recorded, and staff are alerted to the dangers of printing, faxing and emailing sensitive information. Phone conversations with potential research subjects will occur behind closed doors, and staff will ask callers if they are in a location where sensitive information can be discussed without danger of revealing confidential information. Any information gathered on subjects who prove ineligible will be destroyed as soon as possible (a list of patients who have declined or screened out will be maintained through the recruitment phase to avoid contacting these subjects again).

8.2.2 Known Potential Risks and Minimization of Risks

(1) Confidentiality risks and Protected Health Information (rare) - Loss of confidentiality around sensitive information such as psychiatric status, history of substance abuse, etc.

Minimization of Risk:

- Investigators and research staff who are responsible for conduct, management, and oversight of the study will be required to fulfill all training requirements for Good Clinical Practice (GCP). All investigators and research staff will be required to handle protected health information as outlined by the Health Insurance Portability and Accountability Act (HIPAA).
- Confidentiality of participant records is assured by assigning a research code and identifying all computer and paper files only by this code, except for a single tracking file. Paper records are kept in locked drawers in a locked room and electronic records are kept on secure server, to which only authorized research personnel have access.
- Screening forms for subjects who do not qualify for the study will be destroyed, except for anonymous information (such as age, gender and education).
- After the completion of data analysis, the record linking subjects to the research codes will be destroyed, thereby anonymizing the data.

(2) Risk of psychological discomfort, stress, or symptom exacerbation (infrequent) - Risks of psychological discomfort associated with the questions asked in the clinical interview or on some of the questionnaires.

Minimization of Risk:

- During the assessment process, subjects are reminded that they do not have to answer questions that make them feel uncomfortable.
- Participants are also reminded during the study that they may choose to terminate participation at any time throughout the study.

- Staff will check in with the participant frequently to if they are alright. Breaks will be offered to reduce any fatigue or stress.
 - Interested participants will also be provided with a list of counseling resources.
 - Suicide protocol: The suicide protocol begins with assessment of suicidal thoughts, plans, intentions, and behaviors with the C-SSRS (at initial screening). If assessment uncovers suicidal plans or intentions or recent behaviors, emergency evaluation will occur, and an appropriate plan of action will be followed, e. g. referral to psychiatric emergency room. The PI (a licensed clinical psychologist) will be contacted and will join the decision-making process about how to manage the suicidal thoughts or behaviors. Subjects who experience severe symptom worsening, including suicidal thoughts or behaviors, will be withdrawn from the protocol.
- (3) The risks associated with potentially disturbing material (e.g., IAPS and OASIS pictures): There is a risk that subjects may become uncomfortable viewing the negative content of the IAPS and OASIS pictures.

To minimize risk:

- The research team has had extensive experience with the IAPS picture set, in over 200 subjects, including persons with psychiatric diagnoses such as schizophrenia and post-traumatic stress disorder. This image set has been used at laboratories all over the world, and subjects tolerate the images without significant difficulty. The most aversive pictures consist of images that one would encounter in a "very gory R-rated movie," as we explain this to our subjects. The OASIS picture is a well-validated dataset, designed at Harvard, to include updated images with similar content to the IAPS. When we inform our subjects about the study, we remind them they maintain control over their experience, and we encourage them to close their eyes for any image they find too intense. We also remind them that they can terminate the study, at any time. We have presented the images and discussed the protocol with members of the University of Michigan IRB, as well as community members at the local mental health agency. Mindful of potential psychological harm that some images could present for vulnerable psychiatric patients, we have excluded images suggestive of suicidal behavior from those we would present to our subjects. If any participant should become upset while viewing the pictures, the PI would be available to counsel the subjects and reinforce positive coping strategies to deal with the experience.

Risks Associated with fMRI Scanning:

- (4) Discomfort or anxiety (occasional, not serious). There is a minor risk of discomfort or anxiety/panic from being in the confined space of the MRI scanner.

Minimization of Risk:

- The risks of discomfort and anxiety will be minimized by custom pads and pillows to make the subject as comfortable as possible. The subject can communicate with the machine operator via an intercom and may trigger an audible alarm at any time.
- Before the subject rolls into the bore of the magnetic, he or she is always reminded that they are free to stop the study at any time if they become uncomfortable.

(5) Peripheral nerve stimulation (rare, not serious). Fast imaging sequences, such as those employed in this study, have the potential to induce peripheral nerve stimulation (PNS). PNS can be described as a light touching sensation on the skin surface and may cause mild discomfort but is not harmful to the subject.

Minimization of Risk:

- The MRI machine is operated within FDA guidelines so the potential for inducing PNS is low.

(6) Slight dizziness, light-headedness or nausea (rare, not serious). Sometimes subjects report these symptoms during or immediately after the scanning session.

Minimization of Risk:

- If a subject feels light-headed, we will have them get up from the scanner bed very slowly, resting with the feet dangling for several seconds or more before attempting to stand.

(7) Incidental finding: Magnetic resonance image will reveal a minor or significant lesion in the brain, e. g. a tumor, previously unknown to the subject, and requiring additional follow-up. (rare, serious).

Minimization of Risk:

- Subjects will be made aware of the risk of learning about an anomalous finding in the study that might require further evaluation with a clinical MRI study. We will also inform the subject that many abnormalities will not be picked up in this study, since the scanning sequences we use are not sensitive to many forms of brain pathology. However, in the event that we find something that is very obvious, such as a large tumor, the PI will personally inform the subject by phone call, or in person.
- A neuroradiologist is available through the fMRI laboratory to review suspicious findings and provide guidance about the urgency and advisability of clinical follow-up. No diagnosis will be offered, but the P.I. may recommend that the subject pursue a follow-up study with their primary care clinician.
- The PI and study team will facilitate referrals and may provide copies of the brain image if these would be deemed helpful.

(8) Hearing damage - from loud, vibrating noises made by the scanner (very rare, serious).

Minimization of Risk:

- All subjects will wear earplugs and/or earphones throughout the procedure, which attenuate high decibel sounds, but still enable a subject to hear the intercom and respond to questions from the investigator while they are in the scanner.

(9) Injury (very rare, serious). Because the strong electromagnetic fields can move metal objects and cause heating, there is a risk that loose objects (jewelry, keys) outside the body could be accelerated by the magnetic field, striking and injuring a subject. There is also a risk that the magnetic fields could disturb

a metal fragment in the body, interfere with an implanted device, such as a pacemaker or neurostimulator, or cause metal (including foil-backed medication patches) on or in the body to heat up, causing harm.

Minimization of Risk:

- The MRI suite is kept clear of all objects that could be picked up by the magnetic field, and all subjects complete a comprehensive MR screening form prior to entering the scanner, which is reviewed by the MRI technologist (trained in clinical MRI) before scanning begins.

9. Quality Assurance and Audits

9.1 Audits and Inspections

A regulatory authority (e.g. FDA) may wish to conduct an inspection of the study, during its conduct or even after its completion. If an inspection has been requested by a regulatory authority, the study staff must immediately inform IRB, Medical School Regulatory Affairs, MIAP, etc.

9.2 Event Windows, Missed Assessments, Missed Sessions and Protocol Deviation Reporting

Any safety-related assessments (AE Questionnaire, etc.) which are missed will be reported to the IRB as a protocol deviation. For the other assessments, missing assessments will not be reported as protocol deviations unless they constitute > 10% of the total assessments. The time elapsed between the initial assessment and sessions are intended to be approximately 1 week, but scheduling logistics may mean this is not possible for all subjects, and may be longer for some (~ 30 days). These deviations are expected to be minor and will not be reported, although they will be recorded. These allowances should affect neither the scientific integrity nor the safety monitoring provisions of the protocol.

10. References

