4.3.5 Study Visit 4: Follow-up Assessments

Two-week post questionnaires. Two-weeks after the fMRI visit, participants will complete online self-report measures from home via REDcap (see Section 4.5.3). These measures will take 15-20 minutes to complete in total.

One-month post interview. One month after the fMRI visit, participants will complete Study Visit 4, either in person or by phone, with a member of the study staff who is blinded to group assignment. During this study visit, participants will undergo a follow-up interview to assess anxiety symptom severity and complete a series of self-report measures. They will also be asked about how many psychotherapy sessions they attended over the course of the study, as well as the psychotropic medications they are on, to determine if there was a change in dose or a new medication. The visit may take up to an hour.

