4.5 Measures and Assessments

Procedures	Pre-Screening (Pre-Consent)	Visit 1 Eligibility	Visit 2 Baseline + Training	Visit 3 fMRI	Visit 4 2-Week Follow-Up	Visit 5 1-Month Follow-Up
Eligibility				Pre-NF	NF	Post-NF
Phone Screen	X					
Informed Consent		X				
Demographics			X			
Handedness ⁴³			X			
Structured Clinical Interview for the DSM-5 (SCID) ⁴⁷ *		X				
Columbia Suicide Severity Rating Scale (C-SSRS) ⁴⁸ * **		X				X
Treatment Follow-Up						X
Clinical Assessment						
Hamilton Anxiety Rating Scale (HAM-A ⁴⁹) *		X				X
Clinical Global Impressions Scale (CGI) ⁵⁰ *		X				X
Depression, Anxiety and Stress Scales-21 (DASS-21) ⁴⁴			X		X	X
Penn State Worry Questionnaire (PSWQ) ⁴⁵			X		X	X
Emotion Regulation						
Emotion Regulation Questionnaire (ERQ ⁴⁶)			X		X	X
Regulatory Emotional Self- Efficacy Scale (RESE) ⁵¹			X		X	X
Experiences Questionnaire (EQ) ⁵²			X		X	X
Heidelberg Form for Emotion Regulation Strategies (HFERST) ⁵³			X		X	X
Perth Emotion Regulation Competency Inventory (PERCI) ⁵⁴			X		X	X
Beliefs & Personality						

Items from Stanovich Dualism Scale (DS) ⁵⁵			X			X		
Theories of Anxiety Scale (TOA) ⁵⁶			X				X	X
Theories of Intelligence Scale (TOD) ⁵⁷			X				X	X
Temporal Experience of Pleasure Scale (TEPS) ⁵⁸			X					
Task Training								
ERT Training			X					
Pre-NF IAPS Appraisals			X					
Randomization (Arms 2 & 3)			X					
fMRI								
fMRI Safety Screen				X				
Pre-NF Interview				X				
Short form composite of the Marlowe-Crowne Social Desirability Scale (SDS) ⁵⁹			X					
fMRI Neurofeedback Scan					X			
Post-NF Image Appraisals						X		
Post-NF Interview						X		

* = Clinician administered

** = As needed

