Emotion Regulation Task. Half the participants will be randomized to complete the ERT with veritable feedback from the PFC as described in Phase 2. The specific region of interest (dmPFC or vLPFC) will be determined by the results of Phase 2 and arm 1 of Phases 3 and 4. Participants in the sham group will complete the same ERT as the veritable nf-group, however, the thermometer will display a pseudo-random feedback signal. This signal is generated to match the spectral characteristics of true feedback (established from Phase 2), including the same average success rate to control for the rewarding aspects of receiving feedback. As participants are blind to group assignment, inclusion of a sham-group controls for practice effects, fatigue, and learning that may occur without NF. On each trial of the task, a 4s presentation of vLPFC/dmPFC activity (reappraisal trials) or a crosshair (look trials) will appear following the image presentation screen. In the first functional run ('baseline'), participants complete the ERT without NF to establish baseline activity in the two regions of interest (ROIs: vLPFC and dmPFC), based on masks from previous CR meta-analyses (e.g., ^{20,21}). In the middle runs, participants complete the ERT with NF. In the final functional run ('transfer'), participants again complete the ERT without NF to establish ability to implement learning from NF training.

The NF set-up will utilize custom software, developed by co-investigator [name]. This includes motion correction, linear trend removal and spatial smoothing for each image presentation. The BOLD percentage signal change within the ROI is calculated using most recent "reappraise > look" contrast and fed back as a visual display reflecting BOLD signal change. The feedback display shows a thermometer whose minimum is initially set at 0% signal change. Bars fill the thermometer image to correspond to the increase in participant's brain activity using custom MATLAB scripts. On no feedback runs (baseline and transfer), the display shows a crosshair or a static thermometer.

Post-NF interview.

- Difficulty to complete the task
- Comments and suggestions about the task, including appraisals, affect, and arousal ratings of the images
- Perceived control of brain activity and perceived success of CR during NF³⁵
- Tolerability and acceptability of NF
- Manipulation check of group assignment

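### Section 9.2 makes a missed AE Questionnaire reportable, but no scheduled visit contains one; adverse events other than symptom worsening are captured passively, and no summary by arm is planned

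*Combined protocol and SAP*

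**What the plan says.** Section 9.2 divides missed assessments into two classes. For the first, "Any safety-related assessments (AE Questionnaire, etc.) which are missed will be reported to the IRB as a protocol deviation". All other assessments are reported only when the missing ones exceed 10% of the total. The AE Questionnaire is the only member of the first class that is named.

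Section 7.2 says that at the PI's weekly staff meetings "protocol deviations and adverse events will be reviewed", and that the PI hears of serious events once staff learn of them. Section 7.3 has the IRB review adverse events on its own timetable.

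On collection, the Post-NF interview in Section 4.5.2 includes "Tolerability and acceptability of NF". Section 4.3.5 describes the two-week contact as online questionnaires completed at home. At one month, "participants will undergo a follow-up interview to assess anxiety symptom severity and complete a series of self-report measures", and staff blinded to group also ask about psychotherapy sessions and medication changes. The Section 4.5 table shows the latter contact with a row called "Treatment Follow-Up".

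**The concern.** A stated rule depends on an instrument that the schedule does not provide. Staff or an auditor applying Section 9.2 cannot tell what a missed safety assessment is. The reviews in Sections 7.2 and 7.3 have no described source of adverse-event data beyond what happens to come to staff's notice.

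The protocol itself names risks that need not end on scan day. Section 8.2.2 lists symptom exacerbation and distress from the images. The background section warns that, if instruction is brief, neurofeedback can reinforce maladaptive strategies. That last harm could plausibly differ between veritable and sham feedback, although this is an inference and not something the protocol states. In a sham-controlled comparison, a low count of passively reported events would be hard to read: it could mean few events or little asking.

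**Working it through.** No figure in the plan bears on this, and the documents give no adverse-event rate, reporting rate or sample size for the randomized arms. The check is a comparison of sections, with counts.

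**Step 1. Where does the AE Questionnaire appear?**

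- Section 9.2: yes, as the named safety-related assessment.
- Sections 4.3.1 to 4.3.5 (screening and visits): no.
- Section 4.5 table: 0 rows for an adverse-event questionnaire or adverse-event review, at any visit.
- Section 4.5.2 (scan-related measures): no; the nearest item is tolerability and acceptability in the Post-NF interview.
- Section 6: no adverse-event analysis.
- Sections 7 and 8.2: adverse events are reviewed, but no form, question or collection period is described.

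The gap therefore covers every visit, not only those after the scan.

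**Step 2. What with safety content is collected from the scan onwards?**

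| Contact | Items |
|---|---|
| Scan day, Post-NF | Tolerability and acceptability; comments on the task, with affect and arousal ratings of the images |
| Two weeks, online | DASS-21, PSWQ |
| One month, blinded interview and self-report | HAM-A, CGI, C-SSRS (marked as needed), DASS-21, PSWQ, treatment follow-up |

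**Step 3. Which harms does that cover?** Worsening of anxiety or distress is measured at both follow-up contacts, and new or changed treatment at one month. Two things are not solicited after scan day: events of any other kind, and whether an event is thought to relate to the scan, the images or the feedback. For these the described route is passive.

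**Step 4. Can the Section 9.2 rule be applied?** Its only named item is unscheduled. The word etc. allows other members, but nothing says which. The C-SSRS is the obvious candidate, yet the Section 4.5 table marks it as needed, at Visit 1 and at one month, while the suicide protocol in Section 8.2.2 places it at initial screening. Whether an absent one-month C-SSRS is a missed safety assessment cannot be settled from the text.

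**Step 5. What is compared by arm?** Section 6 has one between-arm analysis of anxiety severity after the scan (HAM-A, time by group, baseline and one month). It has 0 analyses or tables of adverse events.

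**The case against.** The strongest reply is that this is a wording slip around a reasonable safety net. Symptom worsening is the harm most relevant to this population. It is measured at two weeks and again at one month, by a blinded interviewer on the second occasion, and Section 8.2.2 treats severe worsening as grounds for withdrawal. Most of the scanner risks in Section 8.2.2 arise during or just after scanning, when staff are present, and both arms have the same scan and task. Because the rule is open-ended, the C-SSRS, the fMRI safety screen and pregnancy testing could all fall under it. Correcting one phrase in Section 9.2 would remove the mismatch.

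Much of this stands, and it rules out several readings that a reader might infer:

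- That adverse events are never asked about after the scan. The scheduled scales, the C-SSRS and the treatment questions contradict this.
- That harms cannot be compared by arm. HAM-A already is, and any reported event could be tabulated by allocation. What is missing is a general question and a stated plan.
- That Section 9.2 is breached for every participant. An assessment that was never scheduled has not been missed.
- That a given share of events would go unrecorded. Nothing in the documents supports a percentage.

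The absence also carries a caveat. The visit text sends the reader to Sections 4.5.1 and 4.5.3, whose headings do not appear in the text as read, and references 60 to 63 (four symptom scales) are not cited anywhere in it. An adverse-event item there cannot be excluded, though the Section 4.5 table lists the measures by visit and shows none.

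What the reply does not answer is that symptom scales neither ask about other events nor ask about relation to the study procedures. Rewording Section 9.2 alone would restore consistency and leave capture passive.

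**Conclusion.** The point holds in a limited form. Section 9.2 and the Section 4.5 schedule conflict: the one safety assessment that the deviation rule names is in no readable visit. Symptom worsening is adequately scheduled for measurement. General adverse events, and their relation to the scan, images or feedback, are not solicited after scan day, and no summary by arm is planned.

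The size is a count: 0 adverse-event rows in the schedule and 0 adverse-event analyses in Section 6. How many events would be lost cannot be estimated from the documents. The conclusion assumes that the unseen Sections 4.5.1 and 4.5.3, if they exist, contain no adverse-event form. The change is worth making, not merely editorial, because it alters what is collected and makes the harms report interpretable. It does not touch the primary outcomes or their analysis.

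**What to change.** Reconcile Sections 4.5 and 9.2 as follows.

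1. Add an AE Questionnaire row to the Section 4.5 table, marked at three existing contacts: post-NF on scan day, the two-week REDCap set, and the one-month blinded interview. Identify the last by name, since Section 4.3.5 numbers it Visit 4 and the table Visit 5. Include a question on relation to the scan, images or feedback.
2. State when collection starts and ends. If the reappraisal practice at Visit 2 is to be covered, since similar negative images are shown there, the scan-day form can ask back to it.
3. In Section 9.2, list which scheduled assessments are safety-related, and say whether the C-SSRS is one. Reconcile the C-SSRS timing between Sections 4.5 and 8.2.2; which timing is right is for the sponsor to decide.
4. In Section 6, add one descriptive table of adverse events by arm (arms 2 and 3), without hypothesis tests.
5. Send the completed forms to the weekly review in Section 7.2.

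If the questionnaire already exists in a section not visible here, steps 1 and 2 reduce to a cross-reference. The cost is a few minutes per participant at each of three contacts and one extra table, with no added visits.
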